Drugs and dosage Commercial available Beta-glucan derived from bakers yeast (S. Cerevisiae): Glucan #300® produced by Transferpoint, Columbia, United States. 2 capsules of 500mg Glucan #300®, daily, for seven days.

Route of administration Oral administration.

Procedures 10 Healthy volunteers will take Beta-glucan 1000 mg daily for seven days, 5 other healthy volunteers will serve as a control group and do not have to take Beta-glucan. The *ex-vivo* responsiveness of leukocytes to various inflammatory stimuli, peripheral blood mRNA expression of genes related to the immune response, epigenetic modifications, the leukocyte capacity to phagocytose and kill the fungal pathogen *Candida albicans*, blood levels of Beta-glucan, and faecal microbiota will be analyzed on different timepoints.

Statistical analysis Descriptive statistics.

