3 STUDY DESIGN

An open-label, intervention pilot-study in 15 healthy human volunteers. In this pilot study, we will enrol 10 subjects who will take Beta-glucan daily for seven days, and 5 subjects who will serve as control group and do not have to take Beta-glucan but who will be analyzed at the same time points as the subjects in the Beta-glucan group.

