4.4 Sample size calculation

The present study is a safety and proof-of-principle pilot study. A power calculation is not warranted, as the extent (and related clinical relevance) of modulation of the innate immune response *in vivo* by the intervention is currently unknown.

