8.2 Descriptive statistics

For the descriptive statistics, values will be given as mean \pm SD or median and ranges, depending on their distribution. For comparisons, paired Students t -tests or Willcoxon-tests for parametric and nonparametric data as appropriate will be used. Changes over time will be analysed using ANOVA repeated measures. A p value <0.05 is considered significant. Statistical analyses will be performed with SPSS 16.0 (SPSS, Chicago, IL) software.

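### Section 8.2 sets paired tests, repeated-measures ANOVA and p<0.05 for a randomised 10 v 5 pilot of unknown effect size, without committing to estimate the between-arm effect and its uncertainty

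*Protocol*

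**What the plan says.** Section 3 sets the size of the groups: "we will enrol 10 subjects who will take Beta-glucan daily for seven days", and "5 subjects who will serve as control group". Section 7.2 says that subjects are randomised to these groups, so a between-arm contrast is available. The primary outcome in section 7.1.1 is TNF-alpha secretion by LPS-stimulated PBMCs, a continuous measure.

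Section 4.4 describes the study in these terms: "The present study is a safety and proof-of-principle pilot study". It continues, "A power calculation is not warranted", and gives the reason: "as the extent (and related clinical relevance) of modulation of the innate immune response" in vivo "by the intervention is currently unknown".

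The study synopsis gives the statistical analysis as "Descriptive statistics" and nothing more. Section 8.2 has the same heading but goes further. It plans mean and SD, or median and range, depending on distribution. It also plans paired t-tests or Wilcoxon tests for comparisons and repeated-measures ANOVA for changes over time, and it states that a p "value <0.05 is considered significant". It does not say whether summaries are split by arm, and it names no group or group-by-time term. Sections 8.1, 8.3 and 8.4 are marked not applicable, so 8.2 is the protocol's whole analysis plan.

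**The concern.** The protocol knows that it does not know how large the effect is, and it has a randomised control group that could supply an estimate. Yet the only inferential output that 8.2 commits to is significance, from comparisons named as paired. A paired test compares a subject with himself. It cannot compare 10 treated subjects with 5 different controls.

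Followed literally, the plan gives a within-arm verdict for Beta-glucan, another for control, and ANOVA p values whose terms are not stated. Two things are at stake. A result above 0.05 could be read as no effect when the data are compatible with a large one. A result below 0.05 in the Beta-glucan arm alone could be read as an effect of Beta-glucan when the arms do not differ.

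**Working it through.** **Inputs.** From the protocol: 10 and 5 subjects (section 3), randomised (section 7.2), threshold 0.05 (section 8.2). Two-sided testing is assumed, since 8.2 does not say. The protocol gives no SD and no target effect, so there is no stated figure to reproduce, and results are in SD units.

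**1. Precision of the randomised comparison.** Half-width of the 95% interval = t(0.975, 13 df) × SD × sqrt(1/10 + 1/5) = 2.160 × 0.548 × SD = 1.18 SD.

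This is also the smallest observed difference that reaches p<0.05. An observed difference of 1.0 SD would be reported as not significant, with an interval from 1.0 − 1.18 = −0.18 SD to 1.0 + 1.18 = 2.18 SD.

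**2. If the outcome is change from day 0.** The unit is then the SD of change. In units of the SD at one time point (taken as equal at both), the SD of change is sqrt(2(1 − r)), where r is the within-subject correlation. The protocol gives no r, so a range is assumed:

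| Assumed r | SD of change | Half-width |
|---|---|---|
| 0 | 1.41 | 1.67 |
| 0.5 | 1.00 | 1.18 |
| 0.7 | 0.77 | 0.92 |
| 0.9 | 0.45 | 0.53 |

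The half-width thus varies about threefold with r. Means and SDs at separate time points do not reveal r, so a reader could not rebuild the interval for change from them.

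**3. On a ratio scale.** For assumed SDs of log change of 0.3, 0.5 and 0.7, the interval is the estimate multiplied and divided by exp(1.183 × 0.3) = 1.43, exp(1.183 × 0.5) = 1.81 and exp(1.183 × 0.7) = 2.29. With log SD 0.5, an observed ratio of 1.0 is compatible with 1/1.81 = 0.55 to 1.81, that is −45% to +81%.

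**4. What a between-arm p value could show.** By the noncentral t with 13 df, power at two-sided 0.05 is 14%, 27%, 39% and 72% for true differences of 0.5, 0.8, 1.0 and 1.5 SD. It reaches 80% at 1.66 SD.

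**5. Separate paired tests when the arms do not differ.** Suppose both arms truly change by the same amount, in units of the SD of change. The chance of p<0.05 in the arm of 10 and not in the arm of 5 is power(10) × (1 − power(5)):

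| Common change | Power, n = 10 | Power, n = 5 | Chance of split verdict |
|---|---|---|---|
| 0.5 | 0.293 | 0.141 | 0.25 |
| 0.8 | 0.616 | 0.281 | 0.44 |
| 1.0 | 0.803 | 0.401 | 0.48 |

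The true between-arm difference is zero in every row. The split arises from chance and from the unequal arm sizes.

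**The case against.** The strongest reply has four parts.

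- **Intervals belong in an SAP.** Effect measures and confidence intervals are often left to an SAP, and none is shown here. This stands: the bare absence of an interval is not the point. The point is what the protocol does fix, namely paired comparisons and a significance threshold for a randomised two-group design.
- **The aim is proof of principle.** The first research question in the introduction asks whether Beta-glucan modulates responsiveness, and a test is a conventional answer. Section 4.4 does not say that the pilot exists to estimate the effect, and nothing in the protocol says that it will size a later trial. A reader might infer that the pilot fails its own purpose. The documents do not support that.
- **The planned summaries carry information.** A reader might infer that the plan offers nothing but per-arm summaries and a verdict and never estimates the effect. That goes too far. Mean and SD, if reported by arm (8.2 does not say), would give a crude between-arm difference at one time point, and an interval could be worked out from it. A paired t-test also computes the SD of change internally. But mean and SD by time point do not give an interval for change from baseline, and a median with range gives none.
- **The wording of 8.2 is loose.** The Wilcoxon test could be meant as the rank-sum test between arms, and the ANOVA could include a group term. Either would compare the arms, but 8.2 says neither, and both are tied only to a p value.

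It is also fair that no go/no-go decision hangs on the threshold, and that 10 v 5 is imprecise however it is reported. The SD is imprecise too: with 13 df its 95% interval runs from 0.72 to 1.61 times the estimate.

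**Conclusion.** The point holds in a limited form. Section 8.2 does not commit to estimating the randomised effect or its uncertainty, although the effect size is the acknowledged unknown. The paired verdicts that it does name can mislead at these arm sizes. The half-width of 1.18 SD follows from 10 v 5, an equal-variance t interval and two-sided 95% confidence. The split-verdict figure of 48% assumes normally distributed changes, the same true change of 1 SD in both arms, and paired t-tests run in each arm. The ratio-scale figures rest on assumed log SDs and only illustrate the size.

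The severity is moderate to minor. The design and data collection are sound for this purpose, and only the stated main result needs changing.

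**What to change.** In section 8.2, and in matching words in the synopsis, state that the main result for LPS-stimulated TNF-alpha is the Beta-glucan versus control difference (or ratio) in change from day 0 at one pre-stated post-baseline time point, with its 95% confidence interval and the SD of change. The sponsor should choose the time point before any data are seen. Section 7.3 lists seven samplings after baseline, and leaving the choice open would allow seven main results. State that p values, paired within-arm tests and the other time points are supportive.

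The cost is one sentence in two places and a few more columns in the results table, with no new subjects, samples or assays. The downside is that the wide interval will show openly how imprecise the pilot is.

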8.3 Multivariate analysis

Not applicable.

8.4 Interim analysis

Not applicable

9 ETHICAL CONSIDERATIONS

9.1 Regulation statement

The study will be conducted according to the principles of the Declaration of Helsinki and in accordance with the Medical Research Involving Human Subjects Act (WMO).

9.2 Recruitment and consent

Subjects will be recruited by posters. They will be informed about the study and asked for their consent by the investigator. Subjects will be given at least one day to consider their decision.

9.3 Benefits and risks assessment, group relatedness

The subjects will not benefit directly from participation to the study. A subject fee is provided.

Blood withdrawal

In total, maximum 360 ml of blood will be drawn, which is not expected to result in side effects. All blood sampling will be performed on blood obtained by venapuncture.

Beta-Glucan

Beta-glucans are commonly available as health food supplements and are considered safe and non-toxic, with the classification of "GRAS" (Generally recognized as safe) by the FDA as a dietary food additive supplement [42] and by the Dutch Medicines Evaluation Board (MEB) [43].

9.4 Compensation for injury

The sponsor/investigator has a liability insurance which is in accordance with article 7, subsection 6 of the WMO.

The sponsor has an insurance which is in accordance with the legal requirements in the Netherlands (Article 7 WMO and the Measure regarding Compulsory Insurance for Clinical Research in Humans of 23th June 2003). This insurance provides cover for damage to research subjects through injury or death caused by the study.

1. \in 450.000,-- (i.e. four hundred and fifty thousand Euro) for death or injury for each subject who participates in the Research;

2. \in 3.500.000,-- (i.e. three million five hundred thousand Euro) for death or injury for all subjects who participate in the Research;

3. \in 5.000.000,-- (i.e. five million Euro) for the total damage incurred by the organisation for all damage disclosed by scientific research for the Sponsor as 'verrichter' in the meaning of said Act in each year of insurance coverage.

The insurance applies to the damage that becomes apparent during the study or within 4 years after the end of the study.

9.5 Incentives

Subjects will be compensated with 200 Euro after completion of the study. If the subject ends participation before completion of the study the subject will receive a proportional share of the total fee. When the subject is forced to stop because of medical reason before the end of the study, the complete amount will be paid.

10. ADMINISTRATIVE ASPECTS, MONITORING AND PUBLICATION

10.1 Handling and storage of data and documents

Data will be handled confidentially and anonymously. A subject identification code list will be used to link the data to the subject. The code is not based on the subject initials and birthdate. The code used will be BG01.XX, where XX is the number of the subject based on the order of the screening visit (first screened subject is BG01.01 etc.).

The key to the code will be safeguarded by the principal investigator.

The handling of subject data in this study complies with the Dutch Personal Data Protection Act (in Dutch: De Wet Bescherming Persoonsgegevens, WBP).

10.2 Monitoring and Quality Assurance

Monitoring will be carried out by an internal monitor of the Radboud University Nijmegen Medical Centre after completion of the study. The stored data in the CRFs, all informed consents, SAE reports and the trial master file will be monitored.

10.3 Amendments

Not applicable.

10.4 Annual progress report

The principal investigator will submit a summary of the progress of the trial to the accredited METC once a year. Information will be provided on the date of inclusion of the first subject, numbers of subjects included and numbers of subjects that have completed the trial, serious adverse events/ serious adverse reactions, other problems, and amendments.

10.5 End of study report

The principal investigator will notify the accredited METC and the competent authority of the end of the study within a period of 90 days. The end of the study is defined as the last patient's last visit.

In case the study is ended prematurely, the sponsor will notify the accredited METC and the competent authority within 15 days, including the reasons for the premature termination.

Within one year after the end of the study, the principal investigator will submit a final study report with the results of the study, including any publications/abstracts of the study, to the accredited METC and the Competent Authority.

10.6 Public disclosure and publication policy

The principal investigator and the coordinating investigator are first and last author of the manuscript. This trial is not sponsored by a pharmaceutical company. Authors have no conflict of interest to declare. The study will be published regardless the results of the trial.

11. STRUCTURED RISK ANALYSIS

11.1 Potential issues of concern

The subjects will not benefit directly from participation to the study. A subject fee is provided.

Blood withdrawal

Maximum 360 ml blood will be drawn, which is not expected to result in side effects. All blood sampling will be performed on blood obtained by venapuncture.

Beta-glucan

Beta-glucans are commonly available as health food supplements and are considered safe and non-toxic, with the classification of "GRAS" (Generally recognized as safe) by the FDA as a dietary food additive supplement [42] and by the Dutch Medicines Evaluation Board (MEB) [43].

12.2 Synthesis

[figure not shown]
At the end of this study, we will have assessed in humans the potential of Beta-glucan as an immune stimulatory compound. This will pave the way towards novel approaches to immunostimulatory therapies in general, and the adjunctive treatment of sepsis in particular. Because oral Beta-glucan is considered safe and non-toxic by the FDA and MEB with no documentation present of any (severe or non-severe) side effects, we feel that the remaining risks for participation in this study are negligible and do not outweigh the scientific and medical relevance of this study.

APPENDIX 1 Flowchart Beta-glucan pilot study
